**Figure 1 Study Design**

**Note:** symbol (  ) Represents interim reporting

The study is planned to collect a broad variety of safety and other clinical parameters data generated during routine clinical care visits and other relevant clinical contacts (e.g. phone calls between patient and clinical site) in AGHD patients treated with commercially available Sogroya® (somapacitan). The duration of the study is planned with patient participation for 5 years or longer up to a total study duration of 10 years, if possible. The main purpose of the study is to observe patients for long-term safety. It is however well known that adult patients on GH therapy, often interrupt or discontinue treatment. Due to this expected dropout from treatment, and in the context of the duration of the study, patients switching from or discontinuing treatment with Sogroya® (somapacitan) will be offered continuation in the study in order to collect post treatment data.

The current study will compare data from a non-interventional registry study (NordiNet® IOS) which was monitoring the long-term use of once daily Norditropin® as a historical comparison group consisting of approximately 2300 AGHD patients enrolled in Europe between 2006 and 2016.

The sample size estimation for this study is based on the incidences for neoplasms reported in Nordinet® IOS. It is estimated that a sample size of 400 patients will be required to rule out the doubling of incidence for neoplasms in patients treated with Sogroya® (somapacitan).

Data on concomitant medication, medical history (adult/ childhood onset of GHD), laboratory parameters including but not limited to hepatic, renal, heart and diabetes status as well as data on neoplasms and medication errors will be collected as part of this study if available per routine clinical practice in order to evaluate safety. Other data which are already available in the medical records or being obtained as part of routine clinical practice, such as IGF- I /IGFBP-3 values, measures of body composition and bone health and PROs, will be collected to support the evaluation of clinical parameters.

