### 9.5 Study sample size

#### Sample size calculations

The following table shows the 95% confidence interval for an incidence between 0% and 5%, like e.g. the incidence of neoplasm:

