**Table 1 Sample size calculations**

Sample size		Observed incidence					
		0%	0.5%	1%	2%	3%	4%
100	<3	-	0 – 5.4	0.2 – 7.0	0.6 – 8.5	1.1 – 9.9	1.6 – 11.3
200	<1.5	0 – 2.8	0.1 – 3.6	0.5 – 5.0	1.1 – 6.4	1.7 – 7.7	2.4 – 9.0
400	<0.75	0.1 – 1.8	0.3 – 2.5	0.9 – 3.9	1.6 – 5.2	2.3 – 6.4	3.1 – 7.6
600	<0.50	0.1 – 1.5	0.4 – 2.5	1.0 – 3.5	1.8 – 4.7	2.6 – 5.9	3.4 – 7.1

Using the observed incidence for neoplasm of 2% in the NordiNet® IOS with somatropin as reference values, a sample size of about 400 patients would be required to rule out the doubling of incidence for neoplasm. In general, the table shows that the precision, i.e. the change for the upper limit of the confidence interval, is having a large decrease when changing from 200 to 400 patients,

Protocol  
 Study ID: NN8640-4515  
 UTN: U1111-1264-8642  
 EU PAS No: Pending

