**CONFIDENTIAL**

Date:	15 February 2022	Novo Nordisk
Version:	3.0	
Status:	Final	
Page:	28 of 53	

while the change from 400 to 600 patients is not having the same impact on the precision. Therefore, the study is planned for the sample size of 400 patients.

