### 9.7.2 Statistical methods

#### 9.7.2.1 Analysis of primary endpoints

The primary endpoints are the number of Adverse Drug Reactions (ADRs), incident neoplasms, and incident T2D from baseline (week 0) up to end of study (week 520).

Frequencies of ADRs during the study period will be summarised by MedDRA SOC and PT. This summary is displayed with number and proportion of patients with at least one event, number of event and event rate (events per 100 patient-years of exposure).

The primary objective of the study is to evaluate safety of once weekly dosing of Sogroya® (somapacitan) in AGHD patients over a study period up to 10 years, and analysis of ADRs will be one of the tools for achieving this. Adverse drug reactions will be analysed using descriptive statistics based on the ‘on treatment’ observation period (primary evaluation) and ‘in-study’ observation period (secondary evaluation) within the study period. The ADRs will be summarised by treatment, MedDRA (Medical Dictionary for Regulatory Activities) system organ class and MedDRA preferred term. The descriptive statistics will include the number and percentage of patients who experienced ADRs, the number of events and rate per 100 person years. ADRs will be listed by treatment and patient with information on severity, relationship to study product and demographics. ADRs with onset before first dosing will be reported in a separate listing.

In addition, incidence rates will be calculated for the endpoints Neoplasm and Diabetes Mellitus type 2.

Results will be reported separately for treatment-naïve and prevalent users of GH replacement therapy, and patients with a history of neoplasia and diabetes mellitus 2 will be addressed in stratified analyses.

For historical reference the primary evaluation, i.e. the on-treatment analysis, will be compared to the same results reported from the Nordinet® IOS database. It is not expected that there will be big differences in the baseline characteristics between the Nordinet® adult population and the population investigated in this study. If there are big differences between baseline characteristics, a matching procedure will be considered when making the comparison. In addition, a sensitivity analysis will be performed, restricting the primary evaluation to a European population only.

Protocol  
 Study ID: NN8640-4515  
 UTN: U1111-1264-8642  
 EU PAS No: Pending

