**CONFIDENTIAL**

Date:  
 Version:  
 Status:  
 Page:

15 February 2022 | **Novo Nordisk**  
 3.0  
 Final  
 48 of 53

Section 2: Research question	Yes	No	N/A	Section Number
2.1.3 The target population? (i.e. population or subgroup to whom the study results are intended to be generalised)				9.2.4 9.7.2.2
2.1.4 Which hypothesis(-es) is (are) to be tested?				
2.1.5 If applicable, that there is no a priori hypothesis?				

Comments:

Section 3: Study design	Yes	No	N/A	Section Number
3.1 Is the study design described? (e.g. cohort, case-control, cross-sectional, other design)				9.1
3.2 Does the protocol specify whether the study is based on primary, secondary or combined data collection?				9.4
3.3 Does the protocol specify measures of occurrence? (e.g., rate, risk, prevalence)				9.1.1
3.4 Does the protocol specify measure(s) of association? (e.g. risk, odds ratio, excess risk, rate ratio, hazard ratio, risk/rate difference, number needed to harm (NNH))				
3.5 Does the protocol describe the approach for the collection and reporting of adverse events/adverse reactions? (e.g. adverse events that will not be collected in case of primary data collection)				11

Comments:

Not applicable for this study

Section 4: Source and study populations	Yes	No	N/A	Section Number
4.1 Is the source population described?				9.2
4.2 Is the planned study population defined in terms of:				
4.2.1 Study time period				6, 9.1

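### The unconditional claim that 400 patients rule out a doubling of neoplasm incidence holds only if at most 8 cases are seen, about a 59% chance when there is no excess risk

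*Protocol*

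**What the plan says.** - Section 9.5 introduces Table 1 thus: "The following table shows the 95% confidence interval for an incidence between 0% and 5"%. The table is laid out by sample size and observed incidence. For 400 patients and an observed 2% it gives 0.9 to 3.9.
- The text below the table continues: "Using the observed incidence for neoplasm of 2% in the NordiNet" IOS as reference, "a sample size of about 400 patients would be required to rule out the doubling of incidence for neoplasm". It adds that precision improves much more from 200 to 400 patients than from 400 to 600, and ends: "Therefore, the study is planned for the sample size of 400 patients".
- Section 9.1 makes the same claim: "It is estimated that a sample size of 400 patients will be required to rule out the doubling of incidence for neoplasms".
- Section 9.1 describes NordiNet IOS "as a historical comparison group consisting of approximately 2300 AGHD patients enrolled in Europe between 2006 and 2016". Section 9.7.2.1 says that the on-treatment results "will be compared to the same results reported from the Nordinet" IOS database, and that incidence rates will be calculated for neoplasm.
- No probability of meeting the doubling criterion is stated. The ENCePP checklist in Annex 2 answers No to "3.4 Does the protocol specify measure(s) of association", and the comment on that part reads as not applicable.

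**The concern.** A reader will take the claim as a property of the design: enrol 400 patients and, if the drug carries no excess risk, a doubling will be excluded. The table shows something narrower, namely the interval that follows if the observed incidence happens to equal the reference. The observed count will vary, and the 2% cell clears the 4% line by only 0.1 percentage point.

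Incident neoplasm is a primary endpoint of a study that the regulator required. If the claim stands, a drug with no excess risk may well miss the stated target at the final report, and those who relied on the target will have had no warning. The 2% is also used as a known constant, although the planned comparison is with a finite cohort.

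**Working it through.** **Inputs.** Two-sided 95% interval, 400 patients and reference 2% (section 9.5); doubling = 2 × 2% = 4%; comparator of about 2300 patients (section 9.1). *Assumption:* 2% × 2300 = 46 comparator cases. The protocol gives neither the count nor the denominator behind the 2%.

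**1. The plan's own figure.** The exact (Clopper-Pearson) upper limit for x cases in n is the 97.5% quantile of Beta(x+1, n−x); the lower limit is the 2.5% quantile of Beta(x, n−x+1). For x = 8, n = 400 this gives 0.87% to 3.90%, which matches the printed 0.9 to 3.9.

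**2. How many cases still exclude 4%.**

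| Cases of 400 | Exact 95% upper limit | Below 4%? |
|---|---|---|
| 7 | 3.57% | yes |
| 8 | 3.90% | yes |
| 9 | 4.23% | no |
| 10 | 4.55% | no |

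**3. Chance of 8 or fewer cases, reference fixed.** X ~ Binomial(400, p), so P(X ≤ 8) = Σ C(400,k) p^k (1−p)^(400−k) for k = 0 to 8.

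| True incidence | P(X ≤ 8) |
|---|---|
| 1% | 0.979 |
| 1.5% | 0.849 |
| 2% | 0.593 |
| 2.5% | 0.330 |
| 3% | 0.151 |

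With no excess risk, the criterion is missed with probability 1 − 0.593 = 0.407.

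**4. Adding the sampling error of the reference (46 of 2300 assumed).** The exact interval for 46/2300 is 1.5% to 2.7%. For 8/400 against 46/2300 the ratio is 1.00, and

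SE(log ratio) = √(1/8 − 1/400 + 1/46 − 1/2300) = 0.379,

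so the 95% interval is exp(±1.96 × 0.379) = 0.48 to 2.10. The exact conditional upper limit is 2.14. A score test against a ratio of 2 gives z = −1.88, one-sided p = 0.030, which is above 0.025. With 7 cases the upper limits are 1.92 (log) and 1.95 (exact), so at most 7 cases are needed. P(X ≤ 7) at 2% is 0.452 with the comparator held at 46 cases. With both cohorts varying at 2%, it is about 0.44 by the log or exact limit and 0.47 by the score test.

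**5. Sensitivity to the assumed comparator size** (2% in each, 8/400 observed, log method).

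| Comparator size | Upper limit of ratio |
|---|---|
| 1000 | 2.25 |
| 1500 | 2.16 |
| 2300 | 2.10 |
| 5000 | 2.04 |
| 10000 | 2.01 |

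**6. If the measure is a rate.** The chance then depends on expected events. With a fixed reference rate and exact Poisson limits:

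| Expected events m | Most events with upper limit below 2m | Probability |
|---|---|---|
| 8 | 8 (15.76 < 16) | 0.59 |
| 12 | 14 (23.49 < 24) | 0.77 |
| 16 | 20 (30.89 < 32) | 0.87 |

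**The case against.** The strongest reply is that this is a precision calculation. Table 1 is headed by observed incidence, so the condition is visible. Section 9.5 gives a second reason for 400, the gain in precision from 200 to 400. The checklist marks hypothesis testing as not applicable, and section 9.7.2.1 plans descriptive statistics and incidence rates. A size chosen for precision needs no power statement. The choice of effect measure and interval may sit in a statistical analysis plan that is not at hand, and sections 9.7.2.1 and 9.9 already provide for possible matching, a European sensitivity analysis and a discussion of comparability.

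Most of this stands as a defence of the number 400. It does not rescue the sentence. The protocol goes beyond precision and says, twice and without condition, that a doubling will be ruled out. A later analysis plan cannot make that claim true, and neither the table heading nor the second rationale corrects it.

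Three stronger readings are tempting but not supported:

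- *That Table 1 is miscalculated at this cell.* It is not; 0.9 to 3.9 reproduces.
- *That the design fails as a matter of fact even at exactly 2% observed.* This needs the assumed 46 of 2300. The margin is narrow (2.10 to 2.14 against 2.00), although step 5 shows the same direction over a wide range of comparator sizes.
- *That the study has a fixed 41% to 56% chance of missing its goal.* Those figures are for a proportion with 8 expected cases. The 2% carries no time unit, follow-up may run to 10 years, and more expected events would raise the chance (step 6). Attrition would lower it: section 9.2.1 plans for all 400 to complete, while section 9.1 expects many to interrupt or stop treatment and the comparison is on-treatment.

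**Conclusion.** The claim is wrong as written in sections 9.1 and 9.5. On the protocol's own interval method, a doubling of 2% is excluded only with 8 or fewer cases in 400. The probability is about 59% at a true 2% and about 15% at a true 3%, given 400 evaluable patients and a fixed reference. Allowing for error in the reference, under the assumption of 46 cases in 2300, the limit falls to 7 cases and the probability to about 44%.

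The cutoff of 8 belongs to the two-sided 95% limit that the protocol uses; a one-sided 95% exact limit would admit 9 cases (3.89%, probability 0.718). The defect lies in the inference and its wording, not in the table cell, and it does not by itself show that 400 is the wrong size. The checklist answer on measures of association is a related mismatch, because the size is argued from a ratio of 2.

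**What to change.** Keep 400 patients. In 9.1 and 9.5 replace the unqualified sentence with a conditional one, for example:

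> With 400 patients the upper 95% limit is below 4% if at most 8 neoplasm cases are observed. If the true incidence is 2%, the probability of this is about 59%, and lower (about 44%, assuming 46 cases in 2300) when the sampling error of the NordiNet reference is included.

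In 9.7.2.1, base any statement that a doubling is excluded on the upper 95% limit of a ratio that carries the error of both cohorts. Add that for incidence rates the probability depends on expected events and follow-up. Bring checklist item 3.4 into line.

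If the sponsor also wants to say which larger increase can be excluded with good probability, one basis should be used throughout. With both cohorts varying and the log method, it is about 74% for 2.5-fold, 79% for 2.6-fold and 82% for 2.7-fold. A figure near 80% for 2.5-fold arises only with the comparator held at 46 cases (10 cases, log upper limit 2.46, probability 0.82), and should not stand beside the 44%.

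The cost is wording only: no extra patients or data, but a less favourable stated claim.

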**CONFIDENTIAL**

Date:	15 February 2022	Novo Nordisk
Version:	3.0	
Status:	Final	
Page:	28 of 53	

while the change from 400 to 600 patients is not having the same impact on the precision. Therefore, the study is planned for the sample size of 400 patients.

## 9.6 Data management

Data management is the responsibility of Data Management at Novo Nordisk.

Novo Nordisk will provide paper/electronic Case Report Forms (CRFs/eCRFs) for capture of study specific patient data. Instructions for completion and correction of CRFs/eCRF will be provided.

The following will be provided as paper Case Report Forms (CRFs):

- Pregnancy and pregnancy outcome form

The following will be provided as paper CRFs to be used when access to the eCRF is revoked or if the eCRF is unavailable:

- NIS Safety form

The physician must ensure that study specific patient data is entered in the CRFs/eCRF as soon as possible, preferably within 5 working days after the visit for non-safety forms. The CRFs will be source data verified, as applicable, on behalf of Novo Nordisk. Once data has been entered, it will be available to Novo Nordisk for data verification and validation purposes.

Appropriate measures such as encryption or deletion must be enforced to protect the identity of patients when transmitting data, in all presentations and publications as required by local/regional/national requirements.

The system for Electronic Data Capture (EDC) and support services for the system will be supplied by EDC system supplier. The activities of EDC system supplier will be under the direction and supervision of Novo Nordisk.

An audit trail will be maintained in the EDC application containing as a minimum: identification of the person entering the data, date and time of the entry and reason for the correction, the original entry, and the corrected entry.

By signing the casebook, the physician confirms that the information in the CRF/eCRF is complete and correct.

If corrections are made by the physician's authorised staff after the date of the physician's signature on the casebook, this must be signed again by the physician.

Available local laboratory data and PRO data will be entered in the eCRF by the physician/site staff.

Site specific eCRF data must after the study database is locked be downloaded by site in an electronic readable format of site's choice. Hereafter access to the study specific EDC will be removed.

Protocol  
 Study ID: NN8640-4515  
 UTN: U1111-1264-8642  
 EU PAS No: Pending

**CONFIDENTIAL**

Date: 15 February 2022 **Novo Nordisk**  
 Version: 3.0  
 Status: Final  
 Page: 29 of 53

## 9.7 Data analysis

### 9.7.1 Definition of analysis sets

The safety analysis will be based on the Safety Analysis Set (SAS). The SAS will consist of all patients exposed to Sogroya® (somapacitan) during study period. Two observation periods are defined:

- on-treatment: from first administration until last study contact, discontinuation of Sogroya®, or withdrawal of informed consent, whichever comes first
- in-study: from first administration until last study contact, or withdrawal of informed consent, whichever comes first

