To enable intra-personal comparison on dose of previous GH treatment, IGF-I/IGFBP-3 SDS values, measures of body composition and bone health and oral oestrogen treatment status, 12-months retrospective data (i.e., from medical charts, where available.) will be collected at study enrolment.

Protocol  
 Study ID: NN8640-4515  
 UTN: U1111-1264-8642  
 EU PAS No: Pending

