**Novo Nordisk**

Additionally, the severity of GH deficiency expressed as IGF-I SDS level prior to any initiation of GH treatment should be collected at baseline, if available.

Data on the number of patients with a minimum of 1-year of follow-up achieving the age-adjusted IGF-I SDS levels up to the upper limit of the normal reference range (0 and +2) will be reported (i) as part of the progress reports in connection with the PSURs - as soon as first data are available and (ii) as part of the interim reporting (data cut 3 and 6 years after FPFV).

Monitoring of safety in this study will be performed from time of enrolment, defined by signing of the informed consent, until the patient's last visit in the study (defined as end of study or withdrawal of informed consent). Adverse events are expected to be captured and reported by the participating sites during routine clinical evaluations (expected every 6-12 months) and any other intermediate contacts with the patient (e.g. phone call etc).

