### 9.2.3 Exclusion criteria

For an eligible patient, all exclusion criteria must be answered “no”.

1. Previous participation in this study. Participation is defined as signed informed consent
2. Mental incapacity, unwillingness or language barriers precluding adequate understanding or cooperation
3. Patients with hypersensitivity to the active substance or to any of the excipients.
4. Patients with active malignancy or in treatment for active pre-existing malignancy.
5. Patients with acute critical illness, suffering from complications following open heart surgery, abdominal surgery, multiple accidental trauma, acute respiratory failure or similar conditions per investigator judgement.

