### 9.2.4 Rationale for selection criteria

The study population is comprised of adult patients diagnosed with GHD and treated with commercially available Sogroya® (somapacitan). The study population will include patients naïve and non-naïve to any GH replacement therapy (including Sogroya® (somapacitan)) at time of study enrolment and will also include patients with severe hepatic impairment, patients with New York

Protocol  
 Study ID: NN8640-4515  
 UTN: U1111-1264-8642  
 EU PAS No: Pending

CONFIDENTIAL

Date: 15 February 2022  
 Version: 3.0  
 Status: Final  
 Page: 20 of 53

Novo Nordisk

Heart Association class 2 heart failure and woman on oral oestrogen treatment who are diagnosed with AGHD.

The few inclusion and exclusion criteria of this study will greatly reduce selection bias. As a multicentre, multinational population has been selected the generalizability of the study is evaluated as high. The study is global and can include all ethnic groups.

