# 11 Management and reporting of adverse events/adverse reactions

## 11.1 Collection of adverse events and other safety information

Safety definitions and a guideline for evaluation of outcome, severity and causality can be found in [Appendix A](#).

All adverse events including all fatal outcomes on Sogroya® (somapacitan) which occur after informed consent is obtained and until the end of study for each participating patient must be collected and reported to Novo Nordisk.

If the physician becomes aware of events of overdose, abuse, misuse, medication errors, lack of therapeutic effect or occupational exposure related to the study product treatment with or without an associated suspected adverse reaction, this should be reported to Novo Nordisk on the NIS Safety Form and on the medication error, misuse and abuse form (misadministration). These events will be summarised by Novo Nordisk in the interim and final study reports.

For female patients: Pregnancies and pregnancy outcome should be collected including **adverse events** in the pregnant patient, foetus or newborn infant from birth to 12 months of age.

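### Both observation periods in 9.7.1 start at first Sogroya dose, but events are captured only from consent, so person-time rates that include patients already on Sogroya are biased low

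*Protocol*

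**What the plan says.** Protocol section 9.7.1 defines two periods for the safety analysis set. The primary one is "on-treatment: from first administration until last study contact", ending earlier on discontinuation of Sogroya or withdrawal of consent. The secondary one is "in-study: from first administration until last study contact, or withdrawal of informed consent, whichever comes first". Neither start refers to consent or baseline.

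Event capture starts elsewhere. Section 9.1 states: "Monitoring of safety in this study will be performed from time of enrolment, defined by signing of the informed consent". Section 11.1 requires reporting of events "which occur after informed consent is obtained and until the end of study for each participating patient must be collected", and section 9.2.7.1 says the same.

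Section 9.2.4 admits "patients naïve and non-naïve to any GH replacement therapy (including Sogroya ® (somapacitan)) at time of study enrolment". Section 9.2.8.8 is consistent with this: it asks for Sogroya dosing at study entry and treats patients naïve to Sogroya as a separate case.

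For the period before enrolment, section 9.1 says "12-months retrospective data (i.e., from medical charts, where available.) will be collected at study enrolment". The items listed there and in 9.2.8.6 are previous GH dose, IGF-I/IGFBP-3, body composition, bone health and oestrogen status. Adverse events are not among them.

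Section 9.7.2.1 reports adverse drug reactions per 100 patient-years and calculates incidence rates for neoplasm and type 2 diabetes. It compares the on-treatment analysis with NordiNet IOS. Section 9.7.2.2 handles AEs, SAEs and medication errors in the same way, for both periods.

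**The concern.** For a patient already on Sogroya at consent, first administration lies before consent. Section 9.7.1 counts the time between the two as observed, yet the capture rules allow no event to be recorded in it. The denominator grows and the numerator cannot, which is immortal time in the usual sense.

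The direction is what makes this worth correcting. The study exists to characterise long-term risk, and the error makes the product look safer. It touches the primary (on-treatment) evaluation, which is the one compared with the historical registry. Section 9.7.3 carries the same approach into both interim reports.

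The planned split into treatment-naïve and prevalent users of GH replacement does not remove the problem. The prevalent stratum combines patients who switch to Sogroya at or after consent with patients already taking it, and the latter keep their pre-consent time.

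**Working it through.** **The plan's own figure.** Section 9.5 rests on an observed neoplasm incidence of 2% in 400 patients, with the interval 0.9–3.9% in Table 1. The exact binomial 95% interval for 8/400 is 0.87–3.90%, so the figure reproduces. It is a proportion of patients with no person-time in it, and this point does not affect it.

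**Dilution of a person-time rate.** Inputs:
- T, mean observed time after consent. Section 9.1 plans five years or longer; 5 years is used here as an assumption. On-treatment time may be shorter, because the same section expects discontinuations.
- f, share of patients already on Sogroya at consent. Not in the protocol; assumed.
- t0, their mean Sogroya exposure before consent. Not in the protocol; assumed.

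With N patients, a constant rate λ and no events captured before consent, the expected number of events is λ·N·T. The denominator under 9.7.1 is N·T + N·f·t0. Hence

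reported rate / true rate = T / (T + f·t0).

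With N = 400 and T = 5, time at risk is 400 × 5 = 2,000 patient-years. The last column shows an illustrative true rate of 2.0 per 100 patient-years, i.e. 40 events.

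| f | t0 (years) | Added patient-years | Factor | 2.0 would read |
|---|---|---|---|---|
| 10% | 0.5 | 400 × 0.10 × 0.5 = 20 | 2000/2020 = 0.990 | 1.98 |
| 25% | 1 | 400 × 0.25 × 1 = 100 | 2000/2100 = 0.952 | 1.90 |
| 50% | 1 | 400 × 0.50 × 1 = 200 | 2000/2200 = 0.909 | 1.82 |
| 50% | 2 | 400 × 0.50 × 2 = 400 | 2000/2400 = 0.833 | 1.67 |

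A shorter T makes the same f and t0 weigh more: with T = 3, f = 50% and t0 = 2 the factor is 3/(3 + 1) = 0.75.

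**By stratum.** In GH-naïve patients t0 = 0 and the factor is 1. All patients already on Sogroya fall in the prevalent-user stratum, so f there is at least as large as in the pooled set and, for the same T, the factor is no closer to 1.

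**Does other wording remove the pre-consent time?** Section 9.7.2.1 confines the two periods to the study period. The only dated study period is the calendar window in 9.2.1, 15 Dec 2022 to 15 Dec 2032, and recruitment runs to 15 Dec 2027 (section 6). A patient first dosed on 15 Dec 2023 who consents on 15 Dec 2027 has four unobserved years inside that window. On this reading the wording only caps pre-consent time, at five years (15 Dec 2022 to 15 Dec 2027).

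**The case against.** The strongest defence is that the authors meant the first dose taken within the study. Several places support this. The endpoint tables in 9.1.1 and the opening of 9.7.2.1 run from baseline (week 0). The analysis set and the periods are tied to the study period. Section 9.7.2.1 lists reactions that begin ahead of the first dose separately, which makes sense only if dosing follows consent. No section explicitly asks for the date of the first-ever Sogroya dose in existing users, which the literal denominator would need.

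This stands as evidence of an inconsistency, so the bias follows from the written definition and is not certain to occur. It does not settle the matter: 9.7.1 is the operative definition, the study period is not defined per patient, and an analysis plan that follows 9.7.1 faithfully would inherit the early start.

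A reader might infer more than the documents support:
- **That all safety rates are biased.** Only patients already on Sogroya at consent add such time. Counts, percentages of patients with events and GH-naïve rates are untouched.
- **That exclusion 4 makes the pre-consent time event-free.** It removes "Patients with active malignancy or in treatment for active pre-existing malignancy". It does not bar type 2 diabetes, a benign neoplasm or a malignancy that has since been treated and is inactive. The general reason no event counts is the collection window.
- **That a doubled rate relative to NordiNet would appear as a specific smaller ratio.** The protocol does not say how NordiNet counted exposure, so no bias in the ratio can be computed.

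**Conclusion.** The point holds for a defined set of results. As written, 9.7.1 biases downward the pooled and prevalent-GH-user person-time rates for ADRs, AEs, SAEs and medication errors. It does the same to the neoplasm and type 2 diabetes incidence rates if they are computed on these periods, which 9.7.2.1 implies for the NordiNet comparison but does not spell out.

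With T = 5 years the rates would be about 1% to 17% too low over the range from f = 10%, t0 = 0.5 year to f = 50%, t0 = 2 years. Those values are assumptions, as is a constant event rate. If few existing users enrol, the effect is negligible. The direction does not depend on these values, provided at least one existing user contributes pre-consent time.

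**What to change.** In 9.7.1, start both periods at the later of signed informed consent (baseline) and first Sogroya administration. For patients already on Sogroya, treat earlier exposure as delayed entry: keep it as time since first dose and do not count it as person-time at risk. Define the study period per patient, and align baseline (week 0) in 9.1.1 and the wording of 9.7.2.1 with the same start. With this start t0 drops out of the denominator and the factor is 1.

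Optionally, report patients already on Sogroya at consent separately from those who start Sogroya at or after consent. This is useful, but not needed to remove the bias.

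The cost is a few lines of text and a somewhat smaller reported exposure, with no new patients or visits. The time-since-first-dose variable needs the date of first Sogroya administration in existing users. If the eCRF does not already hold that date, one field has to be added.
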